Investigational drug	The study drug whose properties are being tested in the study; this definition is consistent with US CFR 21 Section 312.3 and is synonymous with "investigational new drug" or "investigational medicinal product".
Investigational treatment	All investigational drug(s) whose properties are being tested in the study as well as their associated treatment controls. This includes any placebos, any active controls, as well as approved drugs used outside of their indication/approved dosage or tested in a fixed combination. Investigational treatment generally does not include other treatments administered as concomitant background therapy required or allowed by the protocol when used within approved indication/dosage.
Medication number	A unique identifier on the label of each study drug package in studies that dispense study drug using an IRT system.
Non-investigational medicinal Product (NIMP)	Products which are not the object of investigation (e.g. any background therapy administered to each of the clinical trial subjects, regardless of randomization group, rescue medication, active drug run-ins etc.)
Part	A single component of a study which contains different objectives or populations within that single study. Common parts within a study are: a single dose part and a multiple dose part, or a part in subjects with established disease and in those with newly-diagnosed disease.
Patient	An individual with the condition of interest
Patient-Reported Outcome (PRO)	A measurement based on a report that comes directly from the patient about the status of a subject's health condition without amendment or interpretation of the patient's report by a clinician or anyone else
Period	A minor subdivision of the study timeline; divides phases into smaller functional segments such as screening, baseline, titration, washout, etc.
Randomization	The process of assigning trial subjects to investigational drug or control/comparator drug using an element of chance to determine the assignments in order to reduce bias.
Randomization number	A unique identifier assigned to each randomized subject, corresponding to a specific treatment arm assignment

Glossary of terms

Re-screening	If a subject fails the initial screening and is considered as a Screen Failure, he/she can be invited once for a new Screening visit after medical judgment and as specified by the protocol
Screen Failure	A subject who is screened but is not treated or randomized

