Secondary Objectives	To evaluate the improvement of ECF843 vs vehicle in corneal damage by quadrant as assessed by change from baseline in inferior and central corneal fluorescein staining To evaluate the safety of ECF843 vs Vehicle as assessed by incidence and severity of ocular and non-ocular adverse events
Study design	The study will be conducted in 2 parts: Part 1 – efficacy and safety of ECF843 vs vehicle, followed by Part 2 – exploratory assessments of ECF843 vs vehicle.
	Part 1 uses a double-masked design where subjects will be randomized to receive BID or TID treatment with either ECF843 or vehicle for 56 days. For subjects randomized to ECF843, the maximum drug exposure will be up to 28 days.
	Part 2 will be initiated only if safety and efficacy of ECF843 during Part 1 is demonstrated. Part 2 also uses a double-masked design of ECF843 versus Vehicle for 84 days after a 2- week vehicle run-in phase.
Population	This study will enroll adult subjects, 18 years of age or older with at least 6 months history of physician diagnosed moderate to severe dry eye disease in both eyes as defined by entry criteria.
	It is estimated that approximately 800 subjects will need to be screened in Part 1 to have approximately 680 subjects randomized into the 56-day treatment period.
	For Part 2, it is estimated that up to 200 subjects will need to be screened to randomize up to 160 subjects into the 2 treatment arms.
Key Inclusion	1 Written informed consent must be obtained before any assessment is performed
criteria	2 Adult male or female subjects 18 years of age or older
	3 Subjects must be able and willing to follow the protocol and required assessments
	4 At least 6 months history of physician diagnosed dry eye disease in both eyes
	5 Must use, or feel the need to use, artificial tears/gels/lubricants on a regular basis
	6 Tear Break-up Time (TBUT) ≤ 5 seconds in at least one eye (average of 3 consecutive TBUT readings)
	7 Composite corneal fluorescein staining score ≥ 4 (modified National Eye Institue (NEI) scale) in at least one eye (composite score is the sum score of the 5 regions within a single cornea)
	8 PART 1 ONLY: In-office SANDE global ocular discomfort score ≥ 60 (as measured by 100 mm visual analog scale (VAS)

Protocol summary

	9 PART 2 ONLY: In office Eye Dryness Score ≥ 40mm (as measured by 100mm VAS scale)
Key Exclusion criteria	1 Ocular infection (bacterial, viral, or fungal) in either eye within 30 days prior to Screening

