5.1 Inclusion criteria

Subjects eligible for inclusion in Part 1 must meet all of the following criteria at the Screening Visit (i.e., Visit 1).

Subjects eligible for inclusion in Part 2 must meet all of the following criteria at the Screening Visits (i.e., Visit 1) and Baseline Visit (i.e., Visit 2).

- 1. Written informed consent must be obtained before any assessment is performed
- 2. Adult male or female subjects 18 years of age or older
- 3. Subjects must be able and willing to follow the protocol and required assessments
- 4. At least 6 months history of physician diagnosed dry eye disease in both eyes
- 5. Must use, or feel the need to use, artificial tears/gels/lubricants on a regular basis
- 6. Tear Break-up Time (TBUT) ≤ 5 seconds in at least one eye (average of 3 consecutive TBUT readings)
- Composite corneal fluorescein staining score ≥ 4 (modified National Eye Institute (NEI) scale) in at least one eye (composite score is the sum score of the 5 regions within a single cornea)

- 8. **PART 1 ONLY:** In office SANDE global ocular discomfort score ≥ 60 (as measured by 100 mm Visual Analog Scale (VAS)
- 9. **PART 2 ONLY:** In office Eye Dryness Score ≥ 40mm (as measured by 100mm VAS scale)
- 10. Schirmer score ≥ 1 and ≤ 10 mm after 5 minutes in at least one eye
- 11. Subjects with Sjögren's Syndrome must have dry eye (same inclusion criteria as above) associated with a confirmed diagnosis of primary or secondary Sjögren's Syndrome (e.g., diagnosis supported by lab results, positive biopsy, etc., which may be obtained by any qualified physician including rheumatologist, etc).

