6.1.4 Treatment duration

The planned duration of double-masked treatment during Part 1 is 56 days. In Part 2, a 14-day open label vehicle run-in will be followed by 84 days of masked treatment. Subjects may be discontinued from treatment earlier due to unacceptable toxicity, disease progression and/or treatment is discontinued at the discretion of the investigator, Sponsor, or the subject. Refer to Section 9.1 on discontinuation from the study for additional details.

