8.1.1 Information to be collected on screening failures

Subjects who sign an ICF and subsequently found to be ineligible prior to randomization will be considered a screen failure. The reason for screen failure should be recorded on the appropriate eCRF. The demographic information, informed consent, and Inclusion/Exclusion pages must also be completed for screen failure subjects. No other data will be entered into the clinical database for subjects who are screen failures, unless the subject experienced a serious adverse event during the screening phase (see Section 10.1.3 for SAE reporting details). If the subject fails to be randomized, the IRT must be notified within 2 days of the screen fail and that the subject was not randomized.

Subjects who are randomized and fail to start treatment, e.g. subjects randomized in error, will be considered an early terminator. The reason for early termination should be recorded on the appropriate eCRF.

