10.1 Definition of adverse events and reporting requirements

10.1.1 Adverse events

An adverse event (AE) is any untoward medical occurrence (e.g., any unfavorable and unintended sign [including abnormal laboratory findings], symptom or disease) in a subject or clinical investigation subject after providing written informed consent for participation in the study. Therefore, an AE may or may not be temporally or causally associated with the use of a medicinal (investigational) product.

The investigator has the responsibility for managing the safety of individual subject and identifying adverse events.

Novartis qualified medical personnel will be readily available to advise on trial related medical questions or problems.

The occurrence of adverse events must be sought by non-directive questioning of the subject at each visit during the study. Adverse events also may be detected when they are volunteered by the subject during or between visits or through physical examination findings, laboratory test findings, or other assessments.

Adverse events must be recorded under the signs, symptoms, or diagnosis associated with them, accompanied by the following information (as far as possible) (if the event is serious refer to Section 10.1.2):

- 1. Severity grade
- mild: usually transient in nature and generally not interfering with normal activities
- moderate: sufficiently discomforting to interfere with normal activities
- severe: prevents normal activities
- 2. its relationship to the study treatment (i.e., blinded study medication [ECF843 vs Vehicle], as applicable). If the event is due to lack of efficacy or progression of underlying illness (i.e. progression of the study indication) the assessment of causality will usually be 'Not suspected'. The rationale for this guidance is that the symptoms of a lack of efficacy or progression of underlying illness are not caused by the trial drug, they happen in spite of its administration and/or both lack of efficacy and progression of underlying disease can only be evaluated meaningfully by an analysis of cohorts, not on a single subject
- 3. its duration (start and end dates) or if the event is ongoing, an outcome of not recovered/not resolved must be reported
- 4. whether it constitutes a SAE (see Section 10.1.2 for definition of SAE) and which seriousness criteria have been met
- 5. action taken regarding with study treatment (i.e., blinded study medication [ECF843 vs Vehicle], as applicable)
- 6. its outcome

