Subjects will again be asked to sign the informed consent form in order to participate in Part 2 and will be re-screened to determine continued eligibility. If the subject meets all entry criteria, the subject may be randomized to receive either ECF843, at the concentration and posology selected from Part 1, or Vehicle at the same selected posology at a 3:1 ratio for 84 days of treatment. Enrollment for Part 2 of the study will be discussed between the Investigator and the Sponsor prior to initiating screening visits.

Screening: Subjects will be screened for eligibility at Part 2 Visit 1.

Run-in period: Screened subjects will enter a 14-day vehicle run-in period after screening.

**Randomization**: At Part 2 Visit 2 (baseline), subjects must screen for eligibility criteria at Visit 2 again. Only eligible subjects will be randomized into the study treatment. The randomization will be stratified by subjects with a documented diagnosis of Sjogren's syndrome (yes/no). Subjects will be equally randomized to study treatment.

**Treatment period**: The randomized subjects will begin 12 weeks study treatment after randomization. They will attend the following study visits after baseline for treatment: at Day 7, Day 14, Day 28, Day 42 and Day 84. Day 84 is the time point for primary analysis.

Part 2 is double-masked and exploratory. No interim analyses will be performed in Part 2.

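### Read literally, Protocol 8.1.1 keeps non-serious adverse events out of the database for Part 2 subjects who took run-in vehicle and then failed eligibility at Visit 2; other sections say the opposite

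*Protocol*

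**What the plan says.** **The rule.** Protocol 8.1.1 defines the group: "Subjects who sign an ICF and subsequently found to be ineligible prior to randomization will be considered a screen failure". For that group the site enters the failure reason, demographics, consent and eligibility pages. Beyond these, "No other data will be entered into the clinical database for subjects who are screen failures, unless the subject experienced a serious adverse event". The section does not distinguish Part 1 from Part 2.

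**The Part 2 sequence.** Table 8-2 dispenses study drug at Visit 1 (Day -14) and randomizes at Visit 2 (Day 1). SAP 1.1.2 says: "Screened subjects will enter a 14-day vehicle run-in period after screening". Protocol 6.1.4 says: "In Part 2, a 14-day open label vehicle run-in will be followed by 84 days of masked treatment". Protocol 5.1 and 5.2 and SAP 1.1.2 apply the entry criteria again at Visit 2.

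**Other provisions on the same subjects.**
- The Protocol glossary describes a screen failure as "A subject who is screened but is not treated or randomized". Its definition of study treatment takes in any drug, controls included, that the study procedures require.
- Protocol 10.1.1 counts AEs "after providing written informed consent for participation in the study" and requires follow-up until an event resolves or is judged permanent.
- Table 8-2 marks AEs at Visits 1 and 2. Its legend explains the mark as data that go into the clinical database or arrive from a vendor.
- Protocol Section 8 asks for AEs and concomitant medications on the eCRF at the final visit of a subject who leaves the study early.
- Protocol 12.1 admits to Safety Set 2 anyone with at least one dose of study treatment in Part 2.

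**Planned numbers.** For Part 2, "it is estimated that up to 200 subjects will need to be screened to randomize up to 160 subjects".

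**The concern.** The rule in 8.1.1 suits Part 1, where screening and randomization both fall on Day 1 and a screen failure has taken no study product. It does not suit a part with two weeks of dosing before randomization. A site with a Visit 2 failure has one section, titled for that very case, telling it to enter nothing more, and several others telling it to enter AEs.

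If 8.1.1 is followed, whether a run-in event is recorded depends on whether the subject passes Visit 2. The event can itself decide that. Subjects who pass keep their AE records. Those who fail because of something that happened on the drops keep only a failure reason. The record of vehicle safety in the run-in would then be incomplete in a way related to outcome, and 10.1.1 follow-up could not be shown from the database.

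**Working it through.** **Step 1. One subject, traced through each section.** Take a subject who is dispensed vehicle at Visit 1, doses for 14 days, has a non-serious AE and is found ineligible at Visit 2.

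| Source | Status or instruction |
|---|---|
| Protocol 8.1.1 | Screen failure; AE not entered |
| Protocol glossary | Treated, so not a screen failure |
| Table 8-2 | AE recorded at Visits 1 and 2 |
| Protocol 8, early exit | AE and concomitant medications on the eCRF |
| Protocol 10.1.1 | AE counts, and is followed to its outcome |
| Protocol 12.1, literal reading | Member of Safety Set 2 |

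One section says do not enter; the others imply the opposite. The AE row of Table 8-2 carries a footnote 6 whose text is not visible in the available copy, so it could not be checked.

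**Step 2. Can a run-in event cause the failure?** Exclusions 6 (corneal conditions), 8 (active ocular allergy), 14 (corticosteroid use, including during participation) and 20 (any condition the investigator judges disqualifying) can all become true between Visit 1 and Visit 2. Exclusion 1 (ocular infection) and the stability requirement in exclusion 11 (chronic medication) are dated back from Screening. Read literally, they do not catch an event that starts after Visit 1.

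**Step 3. Size of the group.** The plan gives no figure for run-in failures. From its planning numbers:
- Screened but not randomized: 200 - 160 = 40, which is 40/200 = 20% of those screened.
- These are not split between Visit 1 (undosed) and Visit 2 (dosed), so the affected group is 0 to 40.
- Run-in exposure without non-serious AE data is n x 14 days, if each subject completes the run-in.

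| Assumed Visit 2 failures | Share of all dosed, n/(160 + n) | Subject-days |
|---|---|---|
| 0 | 0% | 0 |
| 10 | 5.9% | 140 |
| 20 | 11.1% | 280 |
| 40 | 20.0% | 560 |

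**Step 4. What might be missed (assumed rates).** The documents give no run-in AE rate. If 5% to 20% of the affected subjects have a non-serious AE, the expected number of subjects with an unrecorded event is 0.5 to 2 (10 failures), 1 to 4 (20) or 2 to 8 (40).

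To illustrate selection at the upper limit, assume a 5% rate in the 160 who pass and 15% or 30% in the 40 who fail. The rate in all dosed subjects is then (160 x 0.05 + 40 x 0.15)/200 = 7%, or (160 x 0.05 + 40 x 0.30)/200 = 10%. The recorded rate would be 5%.

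**The case against.** The strongest reply is that this is a drafting conflict and that loss is not established. By the glossary, a dosed subject is not a screen failure at all, and a site reading Table 8-2 or 10.1.1 would enter the event. That stands: loss follows only if 8.1.1 prevails. It does not remove the need to reconcile the sections, because 8.1.1 is where a site would look.

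A second reply is that little is erased. Serious events are entered, and the failure reason and eligibility pages would leave a trace of an event that caused ineligibility. That also stands, although a failure reason carries no severity, causality or outcome.

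Third, Visit 2 also re-applies the thresholds for tear break-up time, staining, dryness and Schirmer score, which a subject may miss by improving on vehicle. Nothing in the documents says that AEs are the main cause of run-in failure. So the loss can be selective, but it is not shown to be strongly so.

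Fourth, a reader might infer that vehicle tolerability is made to look better in the Part 2 results, or that the comparison of ECF843 with vehicle is biased. The documents do not support this. The events precede randomization, and SAP 2.8 presents safety by treatment group, to which these subjects were never randomized. SAP 2.8.1 plans a separate pre-treatment AE summary for Part 1 only. Part 2 is exploratory, and Table 2-1 sets a safety objective for Part 1 alone.

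Finally, 560 subject-days could be set against the planned randomized vehicle arm: 160/4 = 40 subjects x 84 days = 3,360, and 560/3,360 = 17%. That ratio compares different periods and measures bias in no planned estimate. Part 1 alone plans about 680 x 2/5 = 272 subjects x 56 days = 15,232 subject-days in its vehicle arms, of which 560 is 3.7%.

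**Conclusion.** The point holds as a contradiction that should be resolved. Protocol 8.1.1, read literally, bars non-serious AE entry for Part 2 subjects who were dosed in the run-in and found ineligible at Visit 2. This conflicts with the glossary, Section 8, Table 8-2 and 10.1.1. It also leaves people who may belong to Safety Set 2 without non-serious AE data.

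The size is 0 to 40 subjects and at most 560 subject-days. The upper limit assumes that 200 are screened, 160 are randomized, every failure occurs at Visit 2 and each subject completes 14 days of vehicle. Subjects who leave the run-in for reasons other than ineligibility are not clearly covered by 8.1.1.

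It would go too far to say that these events are certain to be lost. What is at stake is the completeness of run-in vehicle safety data and the membership of Safety Set 2. The randomized comparison is not affected, and neither is Part 1.

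**What to change.** Amend Protocol 8.1.1 so that its bar on further data applies only to subjects who received no study product. This brings it into line with the glossary, Section 8, Table 8-2 and 10.1.1. For Part 2 subjects who received any run-in vehicle but were not randomized, for whatever reason:
- enter AEs, concomitant medications and the reason for leaving;
- follow AEs as 10.1.1 requires;
- show them in a run-in AE listing in the SAP;
- state in Protocol 12.1 and SAP 2.2 whether they belong to Safety Set 2.

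No new term for these subjects is needed, since the glossary already excludes treated subjects from screen failures. The cost is a short wording change, entry of existing eCRF pages for at most about 40 subjects, and one listing. No endpoint, sample size or treatment rule changes.

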8.2 Subject demographics/other baseline characteristics

Country specific regulations should be considered for the collection of demographic and baseline characteristics in alignment with CRF.

The following information will be collected/documented at screening visit for each subject:

- Date of birth, age
- Gender
- Race/Ethnicity
- Concomitant medications

- Past relevant medical history and current medical conditions
- Completed clinical assessments
- Ocular assessment

8.3 Efficacy

[figure not shown]
The following assessments are included to evaluate the efficacy of ECF843:

- Ocular hyperemia
- Tear break-up time (TBUT)
- Corneal fluorescein staining
- Conjunctival lissamine staining

8.3.1 Ocular Hyperemia

The investigator will grade conjunctival bulbar redness. Both nasal and temporal inter-palpebral bulbar conjunctival regions will be graded according to the McMonnies redness photographic scale.

Figure 8-1 McMonnies Redness Photographic Scale

8.3.2 Tear Break-Up Time

For individual subjects, TBUT should be assessed by the same examiner at all time points, and must be measured immediately after instillation of the fluorescein dye if performed at that visit.

Fluorescein impregnated strips supplied by the sponsor will be used according to package instructions. One drop of sterile saline, or equivalent, will be applied to the tip of the strip. DO NOT use anesthetic drops to wet the strips. Immediately after application of the wetting drop to the strip, gently flick the excess drop off the end of the strip prior instilling the dye. A new strip should be used for each eye.

Immediately after instillation of the fluorescein, position the subject's head in the headrest of the slit-lamp instrument and instruct the subject not to wipe or dab their eyes, and to gently blink 3 times (avoid forceful blinks), then stare and NOT BLINK. The Investigator will monitor the integrity of the tear film and, using a stopwatch, measure the time from the last blink until the first black (dry) spot appears in the precorneal tear film (record values to 2 decimal points).

Repeat this procedure to obtain three consecutive TBUT measurements.

8.3.3 Corneal Fluorescein Staining

Corneal fluorescein staining will be conducted by the Investigator. For individual subjects, corneal fluorescein staining should be assessed by the same examiner at all visits using the same slit lamp and the same settings. The right eye should be completed first, followed by the left eye.

[figure not shown]
At visits where TBUT is also done, instillation of the sodium fluorescein dye will have already occurred. As long as the corneal staining assessment is done within the specified time frame, no additional instillation of fluorescein dye is required. At visits where TBUT is not done, follow the same procedure as described above for instillation of fluorescein dye to each eye.

Staining will be assessed a minimum of 2.5 minutes and preferably less than 5 minutes after instillation of the dye. Evaluation of the cornea will be done through a slit lamp with use of a cobalt blue filter.

The degree of staining is based on the Corneal Fluorescein Modified NEI Scale. Each of the five regions (as depicted in the diagram, and defined as central (C), superior (S), inferior (I), temporal (T), and nasal (N)) will be graded based on a scale of 0 to 4, with higher scores suggestive of higher degrees of corneal staining (Figure 8-2). The examiner will indicate the appropriate score for each region. If the assessment falls between grades, round up to the higher score. After entry of the scores per region, the total or composite (sum) score for each eye will be automatically calculated (maximum score = 20/eye).

A (+1) will be added to the sum score for any eye with the presence of filaments.

Figure 8-2 Corneal Fluorescein Modified NEI Scale

Grade 0	No staining
Grade 1	Superficial micropunctate staining covering < 25% of the corneal surface
Grade 2	Macropunctate staining AND/OR superficial micropunctate staining covering 25-50% of the corneal surface
Grade 3	Some coalesced macropunctate staining AND/OR superficial micropunctate staining covering 51-75% of the corneal surface
Grade 4	Numerous coalesced macropunctate areas and/or patches AND/OR superficial micropunctate staining covering > 75% of the corneal surface

